8.2.2. Open-label Treatment Period

Eligible subjects will return to the clinic after the screening period (and wash-out period, if applicable) on Visit 2, which is Day 0 of the 8-week, open-label treatment period. Physical examinations including weight and vital sign assessments, clinical laboratory tests, urinalysis, and the CDAI (CD only) will be performed. A urine β -hCG test will be administered to females of childbearing potential. Any AEs and concomitant medications will be recorded. Blood will be drawn for PK, ADA and exploratory analyses (including LIGHT, cytokines, RNA sequencing, and flow cytometry). Subjects with CD will record their daily assessment of well-being, abdominal pain and stool frequency including loose and watery stools daily in their study diary. Subjects with UC will record stool frequency and rectal bleeding daily in their study diary. Diary data will be reviewed for completeness during each visit. Subjects will be re-evaluated to determine whether they meet all inclusion criteria and do not satisfy any of the exclusion criteria.

Eligible subjects will then be enrolled in the study and receive their first dose of MDGN-002 in the clinic. Subjects will receive MDGN-002 as a SQ injection in the abdomen in a zone of 4 to 10 cm from the umbilicus with the injection site rotated with each subsequent dose. The dose of MDGN-002 will be administered every 14 days (\pm 3 days) for 8 weeks. Subjects will be monitored for AEs during the administration of each dose and for 60 minutes after dosing.

Subjects will return to the clinic every 14 (\pm 3) days (Visits 4, 6, 8, and 10) after the first MDGN-002 dose for assessment of safety, PK, and efficacy and to receive the next dose of investigational product, as shown in [Table 1](#). Additional weekly visits between dosing visits (Visits 3, 5, 7, and 9) will occur at which time blood will be drawn for PK analyses, subjects will be provided access to a study diary for diary data collection, and AEs and concomitant medication use will be recorded.

Prior to enrolling subjects in the second dose cohort, all subjects in the first cohort will have reached Visit 4 (Day 14 \pm 3 days) in the study and safety data from those subjects will be reviewed by the Data Monitoring Committee (DMC; as described in [Section 8.4](#)). A recommendation will be provided by the DMC and a decision by the Sponsor whether subjects can be enrolled in the next dose cohort.

8.2.3. Safety Follow-up Visit

Approximately 28 days after the final dose, subjects will have a safety follow-up visit. The safety follow-up visit will be conducted in the clinic with the subject. Any AEs that occurred in the time since the subject's last MDGN-002 dose will be recorded, along with any concomitant medication use.

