8. INVESTIGATIONAL PLAN

8.1. Overall Study Design

This is a Phase 1b, multi-center, open-label, dose-escalation, signal-finding study to evaluate the safety, tolerability, PK and short-term efficacy of MDGN-002 in adults with moderate to severe, active CD or UC who have previously failed anti-TNF α treatment.

Four subjects with Crohn's disease who satisfy all eligibility criteria will be enrolled in each of 2 dose cohorts. The first cohort will receive MDGN-002 1.0 mg/kg SQ every 14 (q14) days. Dose escalation will proceed after all subjects in the first cohort have been enrolled and reached Visit 4 (Day 14 \pm 3 days), the safety data from those subjects has been reviewed by the Data Monitoring Committee, and a decision has been made to progress to the second cohort (see [Section 8.4](#)). The estimated dose escalation for the second cohort is 3.0 mg/kg SQ q14 days, if permitted by safety data review. After dose escalation has taken place 6 additional patients with UC will also be enrolled in the 3 mg/kg cohort.

Each subject's participation will include a screening period, which if required includes a wash-out period for subjects who have received biologic treatment within 12 weeks of the Screening Visit. With the exception of subjects requiring wash-out of the biologic certolizumab pegol (Cimzia), only those subjects without detectable biologic levels after 8 weeks of wash-out will be allowed to enter the study after confirmation of undetectable levels; all other subjects (including those receiving certolizumab pegol [Cimzia]) will be required to complete a full 12-week wash-out period. The wash-out period includes the time period from the last dose received prior to the Screening Visit. Subjects not requiring a biologic wash-out period will be allowed to enter the study after review and confirmation of eligibility at screening. Screening is followed by an 8-week, open-label treatment period, and a safety follow-up visit approximately 4 weeks after the last dose. The maximum study duration is 26 weeks.

Study visits will occur at screening and on Days 0, 7, 14, 21, 28, 35, 42, 49 and 56. The safety follow-up visit will occur on Day 84. The Schedule of Assessments is shown in [Table 1](#).

Table 1 Schedule of Assessments

Assessment or Procedure	Screening Period				Open-Label Treatment Period										Safety Follow-up	

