10. TREATMENT OF SUBJECTS

10.1. Description of Investigational Product

A description of the investigational product is provided in [Section 11.1](#)

Subjects in each dose cohort will receive the investigational product as a single SQ injection in the abdomen in a zone of 4 to 10 cm from the umbilicus with the injection site rotated with each subsequent dose. The dose of MDGN-002 will be administered on Days 0, 14, 28, and 42. After Day 0, injections must occur within \pm 3 days of the scheduled 14-day intervals.

Subjects in the first dose cohort will receive MDGN-002 1.0 mg/kg for the entire 8-week, open-label treatment period. Data from this cohort will be reviewed by the Data Monitoring Committee as described in [Section 8.4](#) before subjects in the second dose cohort can be treated.

Eligible subjects in the second dose cohort will receive MDGN-002 3.0 mg/kg for the entire 8-week, open-label treatment period. Data from the second cohort will be reviewed, as described in [Section 8.4](#), after all subjects have completed the treatment period and its associated assessments.

Any quality issue noticed with the receipt or use of an investigational product provided by the sponsor (deficiency in condition, packaging, appearance, pertaining documentation, labeling, expiration date, etc.) should be promptly communicated to the sponsor, who will investigate.

A potential defect in the quality of investigational product provided by the sponsor may be subject to initiation of a recall procedure by the sponsor. In this case, the investigator will be responsible for promptly addressing any request made by the sponsor, in order to recall the investigational product and eliminate potential hazards.

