12.1.7. Safety Follow-Up

12.1.7.1. Visit 11 (Day 84 [± 3 days])

Subjects will return to clinic 28 days (± 3 days) after Visit 10 or the early termination visit for a safety follow-up visit, as appropriate. Subject will have blood collected for plasma MDGN-002 concentration, PK and ADA analyses. Any concomitant medications and newly occurring AEs since the last visit will be recorded. In addition, ongoing AEs from the previous visit will be assessed and any change in their status will be recorded.

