12.2. Study Duration

The overall study duration is expected to be approximately 26 weeks (including up to 14 weeks of screening [inclusive of wash-out of up to 12 weeks, if required], 56 days of open-label treatment, and a follow-up visit approximately 28 days after the final dose of investigational product).

The planned sequence and maximum duration of the study periods will be as follows:

1. Screening period: approximately 2 weeks
2. Wash-out period, if applicable: Up to 12 weeks from the subject's last dose of biological treatment
3. Open-label treatment period: 56 days (beginning on Day 0 with doses administered q14 days)
4. Follow-up: 28 days after the last dose of investigational product.

The maximum study duration for each subject is approximately 26 weeks.

The maximum treatment duration for each subject is approximately 56 days, with SQ injections beginning on Day 0 and continuing every 14 (± 3) days through Day 42.

Note: Extensions of the screening window to accommodate clinical laboratory re-testing timeframes (excluding endoscopy with biopsy) are permitted as agreed with medical monitor.

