12.3.2.1. Blood Sample Collection and Analysis

Blood samples will be collected within 60 minutes prior to the administration of MDGN-002 on Days 0, 14, 28 and 42 (Visits 2, 4, 6, and 8 respectively) and at any time on Days 7, 21, 35, 49, 56, and 84 (Visits 3, 5, 7, 9, 10, and 11) and processed to plasma (see laboratory manual). Time of PK samples will be recorded in the electronic CRF. A total of 1.0mL plasma (0.5 mL per PK and ADA sample) will be collected from each subject to measure plasma concentrations of

MDGN-002 or ADA samples. Pharmacokinetic and ADA samples will be processed according to the methods and directions set forward in the Laboratory Manual(s) and guidance(s).

Pharmacokinetic and ADA plasma sample analysis will be performed by laboratory defined in the Laboratory Manual(s) and guidance(s), according to their SOPs using a validated enzyme-linked immunosorbent assay (ELISA). Assay and analysis details will be described in the method validation and bioanalytical information.

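### The safety follow-up visit is timed both from the last dose (Day 70) and from Visit 10 or early termination (Day 84), and SAP 9.2 can end the adverse event summary before an early terminator's own Visit 11

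*Protocol*

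**What the plan says.** **Dosing.** Protocol 10.1: "The dose of MDGN-002 will be administered on Days 0, 14, 28, and 42". The last planned dose is therefore on Day 42, and 12.2 also ends the injections on that day.

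**Follow-up timed from the last dose.**
- Protocol 8.1: "a safety follow-up visit approximately 4 weeks after the last dose".
- Protocol 8.2.3: "Approximately 28 days after the final dose, subjects will have a safety follow-up visit".
- Protocol 12.2: "Follow-up: 28 days after the last dose of investigational product". The opening paragraph of 12.2 says the same.

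**Follow-up on Day 84, or timed from Visit 10 or ET.**
- Protocol 8.1, a few lines further on: "The safety follow-up visit will occur on Day 84".
- Protocol 12.1.7.1 puts the visit 28 ± 3 days "after Visit 10 or the early termination visit for a safety follow-up visit, as appropriate".
- Protocol 12.3.2.1 has blood drawn "at any time on Days 7, 21, 35, 49, 56, and 84".
- SAP 2 and SAP 11 give Day 84, or 28 days after ET.

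**Adverse event (AE) collection and summary.** Protocol 12.3.1.6.2 collects AEs up to the final safety follow-up visit and refers to 8.2.3 for that visit. SAP 9.2 summarises treatment-emergent adverse events (TEAEs) through Visit 11 for subjects who completed the study, and to 28 days after the last dose for those who discontinued prematurely. It lists all AEs but summarises only TEAEs. SAP 6.2 defines study completion as completing the follow-up visit.

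**The concern.** Safety is the primary objective, and the follow-up visit closes AE collection. The cross-reference in Protocol 12.3.1.6.2 leads to the section with the last-dose anchor. A site that schedules from that section would close AE collection two weeks before the date given in 12.1.7.1.

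The same two anchors appear in the analysis. Under 12.1.7.1 an early terminator's Visit 11 is 28 days after the ET visit. The second rule in SAP 9.2 stops counting 28 days after the last dose. Whenever ET comes after the last-dose day, the summary closes before that subject's Visit 11. Events in between are collected and listed but appear in no TEAE table. The subjects affected are those who stopped early, including anyone who met the individual stopping criteria in Protocol 8.5.1. The groups are of 4, 4 and 6, so one subject wrongly counted as event-free moves an incidence by 1/6 to 1/4, or 17 to 25 percentage points.

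There is a smaller effect on pharmacokinetics (PK). SAP 10 summarises concentrations by visit, so a Visit 11 mean would mix post-dose intervals if some subjects were sampled near Day 70 and others near Day 84.

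**Working it through.** **Inputs.** Last dose Day 42 (Protocol 10.1, 12.2); Visit 10 on Day 56 (12.1.5.6); visit window ±3 days (12); screening up to 14 weeks (12.2); half-life 18 to 27 days (SAP 5.3).

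**1. The plan's own total.** Protocol 12.2 states: "The maximum study duration for each subject is approximately 26 weeks". Duration = 14 weeks + (follow-up day ÷ 7).

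| Anchor | Follow-up day | Total |
|---|---|---|
| Visit 10 + 28 | 56 + 28 = Day 84 | 14 + 12 = 26 weeks |
| Last dose + 28 | 42 + 28 = Day 70 | 14 + 10 = 24 weeks |

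Only Day 84 reproduces the stated 26 weeks.

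**2. Whether the windows reconcile the dates.** A last dose on Days 39 to 45, plus 28, gives Days 67 to 73. Day 84 ± 3 gives Days 81 to 87. If Visit 10 itself moves within Days 53 to 59, then 28 ± 3 days later is Days 78 to 90. Neither range meets Days 67 to 73.

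**3. Whether a dose at Visit 10 would reconcile them.** Protocol 8.2.2 includes Visit 10 among the visits at which the next dose is given. A Day 56 dose would make Day 84 equal to last dose + 28. However, 10.1 and Table 1 give four doses and the Visit 10 procedures include none, so this is a wording slip.

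**4. The TEAE gap.** Let the ET visit fall *d* days after the last dose. Visit 11 is at last dose + *d* + 28, and the second SAP 9.2 rule stops at last dose + 28. The gap is *d* days, and the omitted share of the time from last dose to Visit 11 is *d* ÷ (*d* + 28). The documents do not fix *d*, so these values are assumed:

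| *d* | Days omitted | Share |
|---|---|---|
| 7 | 7 of 35 | 20% |
| 14 | 14 of 42 | 33% |
| 28 | 28 of 56 | 50% |

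Example for *d* = 14: last dose Day 28 and ET Day 42 give a cut-off at Day 56 and Visit 11 on Day 70.

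**5. Which SAP 9.2 rule applies.** An early terminator who attends Visit 11 has discontinued treatment prematurely, yet meets the SAP 6.2 definition of study completion. Both rules fit. SAP 5.4 treats completed and early-terminated subjects as separate, and nothing says which rule takes precedence. Protocol 13.1.2 defines TEAEs with no end date, so the cut-off is introduced by the SAP, although SAP 14 reports no changes to the protocol's analyses.

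**6. Exposure at the cut-off.** Assuming first-order elimination, the fraction remaining 28 days after the last dose is 0.5^(28/18) = 0.34 to 0.5^(28/27) = 0.49. Subjects still carry a third to a half of the drug when the summary closes.

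**7. PK timing.** On the same assumption, and only if some subjects are sampled on Day 70 and others on Day 84, the concentration ratio is 2^(14/27) = 1.43 to 2^(14/18) = 1.71.

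**The case against.** The strongest reply is that the working instruction is already clear. Section 12.1.7.1 is a numbered, dated procedure, Day 84 is the only study day printed for this visit, and Section 12 sends sites to the schedule of assessments for timing. In 12.2 the last-dose phrase may be shorthand for the end of the 56-day treatment period. AEs are followed to closure, and serious events discovered after the study must still be reported. On SAP 9.2, the definition in 6.2 would make an early terminator who attends Visit 11 a completer, so nothing is cut off. A last-dose cut-off could also be deliberate, and every event is listed in any case. A 28-day gap is unlikely with weekly visits and 14-day dosing.

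Several of these points stand. Many sites may well follow 12.1.7.1. The listings do keep the events. PK sample times are recorded and anti-drug antibody (ADA) results are only listed, so actual intervals can be recovered. Gaps of 7 to 14 days are more plausible than 28, and a share of days is not a share of events.

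The rest does not remove the problem. Follow-up to closure concerns events already recorded, and the late reporting duty covers only serious ones. The 6.2 reading shows that two SAP rules conflict, not that the conflict is settled. The more natural reading of 9.2 treats a subject withdrawn under Protocol 12.1.6 as a premature discontinuation. A listing does not repair a TEAE table that leaves out collected events.

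**Conclusion.** The concern holds. The last-dose timing in Protocol 8.1, 8.2.3 and 12.2 is wrong by 14 days for a subject who completes treatment. Day 84 is the intended date, and this follows from the documents alone.

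In the analysis, an early terminator placed under the second SAP 9.2 rule loses from the summary as many days as lie between last dose and ET. At the more plausible 7 to 14 days, that is 20% to 33% of the time from last dose to Visit 11. These figures rest on an assumed time to ET and on that reading of 9.2. The 50% figure is an upper illustration. The 1.4- to 1.7-fold PK difference arises only if sites sample on different days.

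This should be corrected before database lock. It does not threaten the design: events remain listed and actual sample times are recoverable. It does affect the main tables for the primary objective, in very small groups.

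**What to change.** **Protocol**
- In 8.1, 8.2.3 and 12.2, time the visit as Day 84 ± 3 (28 days after Visit 10, about 42 days after the last dose), or 28 days after the ET visit.
- Keep that visit as the end of AE collection in 12.3.1.6.2.
- Remove Visit 10 from the dosing visits in 8.2.2.

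**SAP**
- In 9.2, summarise TEAEs through Visit 11 for every subject who attends it, including early discontinuations. Keep a last-dose or last-contact rule only for subjects with no Visit 11.
- In 6.2, state whether an early terminator who attends Visit 11 counts as having completed the study.
- Report actual days since last dose alongside the Visit 11 PK and ADA results.

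With these changes the gap is zero for every subject who attends Visit 11. The cost is wording in four protocol sections, the 9.2 rule with its clarification in 6.2, and one derived time variable.

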8.3. Safety Data Review

Each investigator will review all available safety data collected at their site on a weekly basis, and communicate any safety concerns to the sponsor medical monitor. The sponsor medical monitor will review all relevant safety findings with the coordinating principal investigator and DMC as needed.

Special attention will be paid to adverse drug reactions observed in the MDGN-002 preclinical study as well as other common adverse reactions seen with other biologic treatments which include:

MDGN-002 preclinical observation:

- Injection site reactions

Adverse reactions observed with other biologic treatments:

- Potential for increased infection including opportunistic infections (such as tuberculosis)
- Hypersensitivity reactions (including anaphylaxis)
- Immunogenicity
- Malignancy
- Impaired immunization
- CD exacerbation

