8.4. Data Monitoring Committee

An external, independent Data Monitoring Committee (DMC) comprising physicians, scientists and a biostatistician will review the study data at a meeting after all subjects in the first cohort have been enrolled and reached Visit 4 (Day 14 ± 3 days), and after completion of the second cohort. Additionally, ad hoc meetings to assess individual exacerbations of CD or UC meeting Common Terminology Criteria for Adverse Events (CTCAE) Grade 3 or greater as defined in [Section 8.5](#) may be held. The DMC's role is to protect the interests of the subjects in the study and those still to be entered in the study by reviewing information such as safety, tolerability, pharmacokinetic and efficacy data. The DMC's meeting schedule may be adjusted based on recommendations made by the DMC, the amount of incremental safety data, and other practical considerations. The data provided to the DMC may not be monitored and will not be considered "clean" until the database is locked at the completion of the study.

Possible outcomes of the DMC review can include one of the following recommendations:

- Study can continue
- Study can continue with modifications
- Study is to be terminated

Data Monitoring Committee recommendation will be documented in meeting minutes which will include, at a minimum:

- List of meeting participants
- Summary of data considered during the meeting
- Summary of the DMC recommendation regarding further dose cohorts, including any concerns raised

The sponsor is responsible for the decision to continue, modify or terminate the study. A copy of the DMC meeting recommendation and sponsor decision will be sent to the study sites upon completion and prior to administration of the next subject dose in the second cohort.

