8.5. Individual Subject and Study Stopping Criteria

8.5.1. Individual Subject Stopping Criteria

The following individual subject stopping criteria will be used during the study and will be assessed starting post-dose at Visit 2:

- A subject develops a CTCAE Grade 3 or higher of the following:
 - Injection site reactions
 - Opportunistic infections (i.e. tuberculosis)
 - Hypersensitivity reactions (e.g. allergic reactions, anaphylaxis or cytokine release syndrome)
 - Malignancy
 - Decreased white blood cell count
 - Decrease neutrophil count
 - Decreased platelets
 - Colonic or ileal hemorrhage
 - Colonic, ileal or small intestine obstruction
 - Colonic, ileal or small intestine perforation
 - Colonic, ileal or small intestine stenosis
- A subject will also be stopped if liver enzymes are:
 - ALT or AST >8x ULN
 - ALT or AST >5x ULN for more than 2 consecutive weeks or
 - A single subject ALT or AST >3x ULN with the appearance of fatigue, nausea, vomiting, right upper quadrant pain or tenderness, fever, rash and or eosinophilia (>5%).

Note: subjects who exhibit ALT or AST >3x ULN without appearance of any of the above symptoms must have repeat testing within 48-72 hours to confirm abnormality and determine direction (increase or decrease) from the original value.

- A subject will be stopped if Hy's Law is detected (i.e. ALT or AST >3x ULN and total bilirubin >2x ULN and no other reason can be found to explain the combination of increased AT and TBL, such as viral hepatitis A, B, or C; preexisting or acute liver disease; or another drug capable of causing the observed injury).

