8.5.2. Study Stopping Criteria

The following study stopping criteria will be used during the study:

- The study will be stopped if two or more subjects develop the same CTCAE Grade 3 or if one subject develops a CTCAE Grade 4 of the following:
 - Injection site reactions
 - Opportunistic infections (i.e. tuberculosis)
 - Hypersensitivity reactions (e.g. allergic reactions, anaphylaxis or cytokine release syndrome)
 - Malignancy

- Decreased white blood cell count
 - Decrease neutrophil count
 - Decreased platelets
- The study will be stopped if two individual subjects develop any of the following liver toxicities:
 - ALT or AST >8x ULN
 - ALT or AST >5x ULN for more than consecutive 2 weeks or
 - ALT or AST >3x ULN with the appearance of fatigue, nausea, vomiting, right upper quadrant pain or tenderness, fever, rash and or eosinophilia (>5%).
- The study will be stopped if one subject meeting Hy's Law is detected (i.e. ALT or AST >3x ULN and total bilirubin >2x ULN and no other reason can be found to explain the combination of increased AT and TBL, such as viral hepatitis A, B, or C; preexisting or acute liver disease; or another drug capable of causing the observed injury).
- Individual reports of exacerbations of Crohn's disease CTCAE Grade 3 or greater, such as:
 - Colonic or ileal hemorrhage
 - Colonic, ileal or small intestine obstruction
 - Colonic, ileal or small intestine perforation
 - Colonic, ileal or small intestine stenosis

will be reviewed by the DMC at the first available date after report to determine if modifying the study or stopping the study is recommended.

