8.8. Treatment Assignment

The first cohort of subjects will be assigned to the 1.0 mg/kg dose of MDGN-002. Subjects will be assigned to the second dose cohort, after the DMC review of the safety data from the first cohort, as described in [Section 8.4](#), provided study stopping criteria have not been met as described in [Section 8.5.2](#) and a decision is made by the Sponsor that enrolment can continue.

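### A non-serious event that meets a study stopping criterion can take about a week to reach the sponsor, while subjects at other sites can still be dosed

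*Protocol*

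**What the plan says.** Protocol 8.5.2 sets study-wide stops. "The study will be stopped if two or more subjects develop the same CTCAE Grade 3" event from a list that covers injection site reactions, opportunistic infections, hypersensitivity, malignancy and falls in white cells, neutrophils or platelets. One Grade 4 event from that list also stops the study, as do two subjects with a listed liver toxicity or one subject meeting Hy's Law. The synopsis allows up to 20 centers for about 14 subjects.

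Information reaches the sponsor by these routes:

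- **8.3.** Each investigator is to "review all available safety data collected at their site on a weekly basis, and communicate any safety concerns to the sponsor medical monitor". Then: "The sponsor medical monitor will review all relevant safety findings with the coordinating principal investigator and DMC as needed".
- **12.3.1.6.6.** SAEs go to the sponsor and CRO within 24 hours of awareness. Pregnancy has its own 24-hour rule (12.3.1.6.7.2).
- **12.3.1.5.8.** Clinically relevant laboratory changes are discussed with the medical monitor and recorded as AEs. No time is given.

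On decisions and notices, 8.4 states: "The sponsor is responsible for the decision to continue, modify or terminate the study". It adds: "A copy of the DMC meeting recommendation and sponsor decision will be sent to the study sites"; this follows a DMC meeting and precedes the next second-cohort dose. Under 12.3.1.6.8, active sites are told of related, unexpected SAEs. Under 8.8, subjects are assigned to the second cohort "provided study stopping criteria have not been met as described in" 8.5.2.

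**The concern.** The stopping rule counts across sites, but an investigator sees only one site. The individual rule in 8.5.1 stops the affected subject and does nothing for subjects elsewhere. They are protected only when the sponsor learns of the event and tells the other sites.

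Protocol 12.3.1.6.3 says that severity and seriousness are different things, so a listed Grade 3 event is not automatically an SAE. If it is not, the 24-hour clock does not run and the report moves at the pace of a weekly site review. Safety is the primary objective and this is the first study of the drug in these patients. What is at stake is an injection given at one site after events elsewhere have already met the study's own condition for stopping.

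**Working it through.** The plan states no figure on this point. The check is a comparison of the reporting provisions, followed by simple bounds.

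**1. Which routes carry a deadline for telling the sponsor or CRO?**

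| Provision | Covers | Deadline |
|---|---|---|
| 12.3.1.6.6.1, 12.3.1.6.6.3 | SAEs | 24 hours from awareness |
| 12.3.1.6.7.2 | Pregnancy | 24 hours from awareness |
| 8.3 | Any safety concern | Weekly site review; none stated for the communication |
| 12.3.1.5.8 | Relevant laboratory changes | None |
| 14.2.1 | eCRF entry | As soon as possible; no number of days |
| 8.5.1 | ALT/AST >3x ULN without symptoms | "must have repeat testing within 48-72 hours to confirm abnormality": a time to retest, not to report |
| 8.5.2, Crohn's exacerbations | Grade 3 or greater | "will be reviewed by the DMC at the first available date after report": runs from the report, not from awareness |
| 12.3.1.6.7.3 | Overdose, medication error and similar | SAE route, but the 24 hours apply only if an SAE results |

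No adverse events of special interest are defined (12.3.1.6.7.1), so there is no other fast route. The visit procedures refer only to the individual criteria in 8.5.1. The one explicit operational check of 8.5.2 is in 8.8, before assignment to cohort 2. Under protocol 8.4 and 10.1 the scheduled DMC meetings come after cohort 1 reaches Visit 4 and after cohort 2 completes treatment. None is scheduled while cohort 2 is being dosed.

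**2. Would one site see both counted events?** Planned subjects are 4 + 4 + 6 = 14, and 14/20 = 0.7 per site if all centers open. If two affected subjects are equally likely to be at any of S sites (an assumption), the chance that they are at different sites is 1 − 1/S: 0.80 for 5 sites, 0.90 for 10 and 0.95 for 20.

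**3. Most injections per subject in a week.** Doses fall on Days 0, 14, 28 and 42, ±3 days. The shortest gap is (28 − 3) − (14 + 3) = 8 days if windows run from Day 0, or 14 − 3 = 11 days if they run dose to dose. Both exceed 7, so each other subject in dosing can receive at most one injection per week of delay.

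**4. Planned average.** 14 × 4 = 56 injections. From 2Q2017 to 3Q2022 is about 5.0 to 5.5 years, or 260 to 286 weeks. 56/260 = 0.22 and 56/286 = 0.20, so about 0.2 injections per week study-wide. For the UC group alone, assume that enrolment began with the 23 July 2021 protocol version cited in the SAP. Then 6 × 4 = 24 doses over 49 to 62 weeks (to the start or end of 3Q2022) is 0.49 to 0.39 per week.

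**5. What a deadline changes.** With k other subjects in dosing, a delay of D days admits on average k × D/14 doses.

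- D = 7: 1.0 for k = 2 and 2.0 for k = 4.
- D = 1: 0.14 for k = 2 and 0.29 for k = 4.

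A 24-hour limit cuts exposure during the reporting interval to one seventh of that under a week's delay.

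**The case against.** The strongest reply is that the plan already covers most of this.

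- **A weekly limit is implied.** The duty to communicate sits in the same sentence as the weekly review, and 8.3 singles out injection site reactions for attention. That is a fair reading, and it is why the delay is put at about a week and not left open-ended. A week is still long enough for a dose elsewhere.
- **The stop is unconditional.** Further dosing after 8.5.2 is met would go against that section. True, but a site can obey the rule only once it knows, and some lag will remain under any deadline. The question is whether it should be a day or a week.
- **Most listed events would be SAEs.** Grade 4 events nearly always would be, and the important-medical-event clause mentions blood dyscrasias. This stands and narrows the point to the three groups named above.
- **Liver detection depends on sampling.** After baseline, liver panels are scheduled only at Visits 6 and 10/ET (Table 1, footnote h). This also stands: faster reporting does not shorten the time to detection.
- **Other documents may fill the gap.** The SAP (section 13) refers to a DMC charter, and the protocol refers to laboratory manuals. Neither is available here.

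A reader might also infer that nobody is responsible for the cross-site count. The documents do not support that. All concerns go to one sponsor medical monitor, the sponsor owns the decision (8.4), and open-label data are to be monitored continually (13.1.2). With 14 subjects the count falls to the sponsor in practice.

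**Conclusion.** The point holds in limited form. For a non-serious event that meets a criterion, the plan sets a weekly cadence at best before the sponsor knows. No text ties a notice to hold dosing to 8.5.2 being met. A subject at another site can therefore be dosed in the interval.

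The expected number of such doses is small. The planned average is about 0.2 injections per week study-wide, and the limit is one per week for each other subject in dosing. The average assumes the synopsis dates and even enrolment. It is not an upper bound, because clustered enrolment would raise it. How often the situation would arise cannot be estimated, since the documents give no event rate and no reporting delay.

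A reader might multiply the weekly limit by nearly all planned subjects and infer 8 to 12 stray injections per week. That needs cohort 2, or all 14 subjects, to be in dosing together. Under 8.1, escalation waits until all of cohort 1 reaches Day 14 and the DMC has reviewed the data, and UC enrolment follows escalation. The planned average is far lower.

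This is a modest safety-conduct improvement that does not affect the analysis.

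**What to change.** Leave the stopping criteria as they are and add two requirements in 8.3 and 8.5:

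1. Any event or laboratory result that meets an 8.5.1 or 8.5.2 criterion, whatever its seriousness, is reported to the medical monitor and CRO within 24 hours of the site's awareness, using the SAE contact route.
2. As soon as 8.5.2 is met, the sponsor tells all sites to hold dosing.

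Naming the medical monitor as keeper of the running count would be a useful clarification, but no more than that.

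The route already exists: 12.3.1.6.7.3 sends some non-serious reports along it. That section expressly withholds the 24-hour clock from those reports, so the deadline would be a new obligation and cannot be presented as existing practice. The cost is a short protocol change and a few extra notifications, some for events that never complete a count. No visits, tests or thresholds change, and the new hold on dosing at other sites applies only once 8.5.2 is met.
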